#### **18.3.4. Vital Signs**

Vital signs (BP [systolic and diastolic], heart rate, respiratory rate, and temperature) will be summarized by treatment group and protocol specified collection time point. Observed values and changes from baseline will be presented (descriptive continuous data analysis).

#### **18.3.5. Electrocardiograms**

ECG values will be summarized by treatment group and protocol specified collection time point. Observed values and changes from baseline will be presented (descriptive continuous data analysis). ECG interpretation (Normal, abnormal not clinically significant and abnormal clinically significant) will be tabulated by visit and treatment group in frequency tables (descriptive categorical data analysis).

#### **18.3.6. Ophthalmologic Assessments**

Observations from ophthalmologic assessments will be summarized by protocol specified time point. Observed values and changes from baseline, summarized by treatment group, visit, and study and contralateral eye, will be presented (descriptive continuous data analysis).

The ophthalmologic assessments that will be summarized are listed below:

- Center-Subfield Macula Edema (center-subfield measure)
- Macular fluid volume
- BCVA using the ETDRS visual acuity scale
- FFA
- Corneal thickness based on pachymetry
- Corneal endothelial cell count
- CMT, macular volume, sub-retinal fluid, in the study and contralateral eye as assessed by SD-OCT
- Retinal anatomy as assessed by fluorescein angiography (leakage area) in the study eye and contralateral eye
- DRSS
- Proportion of subjects with a change from baseline value of  $\geq 5$ , 10 and 15 ETDRS letter score (gain or loss) in the study eye versus contralateral eye
- Proportion of subjects who require anti-VEGF therapy in the study and contralateral eye during the study and need for anti-VEGF in the study eye at Day 85 (Visit 7E) and follow-up, as data permit
- Observations via CFP
- Observations via SD-OCT. To evaluate the following ETDRS grid sectors :

- Central subfield
- Inner inferior, inner nasal, inner superior, and inner temporal sectors
- Outer inferior, outer nasal, outer superior, and outer temporal sectors
- Retinal thickness

- Automated Perimetry

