### 7.2.2. Safety

Secondary endpoints that relate to safety are:

- Changes from baseline in Center-Subfield Macula Edema (center-subfield measure)
- Changes from baseline in macular fluid volume
- Change from baseline in BCVA using the ETDRS visual acuity scale
- Change from baseline in FFA
- Change from baseline in corneal thickness based on pachymetry assessed at a consistent time of day
- Change from baseline in corneal endothelial cell count (dose expansion cohort)

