#### *Analysis and Adaptive Design*

All visit-based data will be analyzed for the study eye at each visit and assessed for any change from baseline. Comparisons with the non-dosed contralateral eye will also be evaluated in each subject. All protocol evaluations will also be completed on the non-dosed contralateral eye. No vehicle-control or other study treatments will be administered to the contralateral eye. The response to active treatment will be compared to vehicle on a group basis (pooling vehicle subjects).

The protocol is adaptive regarding the number and size of cohorts and dose level progression, which will be informed by emergent data and recommendation by the DEC following review of available safety and tolerability data from each cohort. The number of dose levels proposed in this protocol can potentially be reduced or altered based on DEC review and Sponsor decision.

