## 8.2. Number of Subjects

Up to approximately 48 subjects will be enrolled into this study.

- Three (3) subjects are expected to be randomized to low-dose, 2 subjects are expected to be randomized to placebo (cohort 1, N=5 total)
- Three (3) subjects to mid-dose, 1 subject to placebo (expected to be cohort 2, N=4 total)
- Three (3) subjects to high-dose, 1 subject to placebo (expected to be cohort 3, N=4 total).

The remaining subjects (up to 40 additional subjects) will potentially be assigned to additional cohorts of four subjects at a given dose level (three EXN407 subjects, one placebo subject), and the remainder will be assigned to the dose expansion cohort once the highest well-tolerated dose is identified. Decisions to escalate to the next higher dose level, to recruit an additional cohort at the same dose level, or to move to the dose expansion cohort, are dependent on emergent data and the outcome of near real-time safety review by the DEC. An algorithm regarding progression to cohort expansion will be defined in the DEC charter.

The sample size for this study is deemed to be sufficient to evaluate the safety and tolerability of EXN407 in this population and to gather efficacy data that will aid in powering future clinical trials.

The final number of subjects is dependent on whether any dose levels are expanded following evaluation of emergent data by the DEC but is not expected to exceed approximately 48 enrolled subjects in total.

As the main aim of this study is to generate information on the safety and tolerability of EXN407, subjects who are withdrawn from the study for reasons other than safety issues may be replaced at the discretion of the Sponsor and the Investigator.

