## 18. STATISTICS

A detailed methodology for the statistical analyses of the data collected in this study will be documented in a statistical analysis plan (SAP), which will be signed off prior to the database lock. All computations will be performed using SAS® version 9.2 (SAS Institute, Cary, NC). Since the primary objective of the study is to evaluate ocular safety and tolerability, no formal hypothesis testing will be performed for any continuous or categorical variables. All statistical analyses will be descriptive in nature and any statistical inference will be carried out according to the analysis plan and interpreted in view of the exploratory nature of the study.

Descriptive statistics (number non-missing values [n], arithmetic mean, SD, 95% confidence interval for mean [where specified], median and range) will be used to summarize continuous variables. Frequencies and percentages will be used to summarize categorical variables. The summaries will be presented by treatment group/cohort and nominal visit/time point (where applicable). Data from the placebo subjects will be pooled (if appropriate).

Baseline demographics and disease characteristics, safety, and [REDACTED] will be summarized descriptively by treatment group and for all subjects combined. Plasma concentrations of EXN407 will be summarized by treatment group and protocol specified time point, and PK parameters calculated where relevant.

Unless stated otherwise, unscheduled data will not be included in the descriptive summaries.

All subject data will be presented in individual subject data listings. Unless otherwise stated, unscheduled visit results will be included in date/time chronological order, within subject listings only. All listings will be sorted by treatment group, subject number, date/time and visit.

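### Section 18.3.6 reports CMT, macular fluid volume and BCVA by arm as observed values and raw changes; no readable text specifies an EXN407 minus vehicle difference with an interval

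*Combined protocol and SAP*

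**What the plan says.** Section 7.2.2 lists the secondary endpoints that relate to safety. They include "Changes from baseline in Center-Subfield Macula Edema (center-subfield measure"), macular fluid volume and BCVA, each as a change from baseline. Section 18.3.6 gives their analysis: "Observed values and changes from baseline, summarized by treatment group, visit, and study and contralateral eye, will be presented (descriptive continuous data analysis").

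Section 18 sets the general approach. It states that "no formal hypothesis testing will be performed for any continuous or categorical variables" and that "All statistical analyses will be descriptive in nature and any statistical inference will be carried out according to the analysis plan". Among the descriptive statistics it lists a "95% confidence interval for mean [where specified"]. Section 18.3.6 specifies no such interval, and no readable section mentions an interval for a difference.

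Two other statements ask for more than tables by arm. Section 8.1 (Analysis and Adaptive Design, repeated in the Synopsis) says: "The response to active treatment will be compared to vehicle on a group basis", with vehicle subjects pooled. Section 8.2 says that the sample should allow the study "to gather efficacy data that will aid in powering future clinical trials".

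**The concern.** The trial is randomized and vehicle-controlled, and the expansion cohort has concurrent vehicle subjects. Its natural product for these endpoints is a difference between arms with an interval. Section 18.3.6 instead stops at one column per arm, so a reader who wants the effect must subtract two means.

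Within-arm changes are a poor substitute. Eligibility requires CMT inside a 280-420 µm window, so mean change in either arm can include regression to the mean. If a pre-dose BCVA is repeated, the best reading becomes the baseline, which pushes later change downward. A randomized contrast removes whatever part of these effects is common to both arms.

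At stake is the usefulness of the data for the purpose stated in Section 8.2. A later sample-size calculation needs an effect estimate, its uncertainty and a residual SD. None of the three is named as an output in the readable text.

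**Working it through.** **What the plan states numerically.** The only sample-size figure is about 48 subjects (Section 8.2). There is no power, effect size, SD or precision target to reproduce. The planned parts add to 5 + 4 + 4 + 40 = 53, not 48. Both figures are upper limits. Holding 48 leaves 48 − 13 = 35 for expansion. With six escalation cohorts (5 + 5 × 4 = 25 subjects) it leaves 23. The sections should be reconciled; here this affects only the n.

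**Inputs.**
- Expansion cohort: at most 40, randomized 2:1 (Synopsis; Section 6.4.3), so about 27:13. Then f = √(1/27 + 1/13) = 0.3376.
- CMT window: 280-420 µm (inclusion criterion 7). If baseline is uniform over the window (assumption), its SD is 140/√12 = 40.4 µm.
- Not in the documents, so assumed: correlation r between baseline and follow-up of 0.3-0.95; or slope b of follow-up on baseline of 0.5-1.0 with residual SD s of 30-60 µm; no dropout.

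**95% half-width of the difference, in SD units** (equal SD at baseline and follow-up):
- Raw change: t(N−2) × √(2(1−r)) × f
- Baseline-adjusted: t(N−3) × √(1−r²) × f × √(1 + 1/(N−4))

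At r = 0.5 and N = 40, raw change gives 2.024 × 1.000 × 0.3376 = 0.683. Adjusted gives 2.026 × 0.866 × 0.3376 × 1.014 = 0.601. The adjusted interval is 1 − 0.601/0.683 = 12% narrower.

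| r | Raw change | Adjusted | Narrower by |
|---|---|---|---|
| 0.3 | 0.809 | 0.661 | 18% |
| 0.5 | 0.683 | 0.601 | 12% |
| 0.7 | 0.529 | 0.495 | 6% |
| 0.8 | 0.432 | 0.416 | 4% |
| 0.9 | 0.306 | 0.302 | 1% |
| 0.95 | 0.216 | 0.217 | none |

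Simulation of 20,000 trials at 27:13 agreed: 12.2%, 6.4% and 1.1% at r = 0.5, 0.7 and 0.9, with coverage of about 95% for both methods. At N = 35 (23:12) the gains are 12%, 6% and 1% at the same values of r.

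**CMT in µm.** Follow-up CMT is not confined to the entry window, so equal variances may fail, and the slope is then the relevant quantity.
- Raw change: t(38) × √(s² + (1−b)² × 40.4²) × f
- Adjusted: t(37) × s × f × √(1 + 1/36)

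At s = 40 and b = 0.5, raw change gives 2.024 × 44.8 × 0.3376 = 30.6 µm. Adjusted gives 2.026 × 40 × 0.3376 × 1.014 = 27.7 µm.

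| s (µm) | b | Raw change | Adjusted | Effect of adjusting |
|---|---|---|---|---|
| 30 | 0.5 | ±24.7 | ±20.8 | 16% narrower |
| 40 | 0.5 | ±30.6 | ±27.7 | 9% narrower |
| 40 | 0.7 | ±28.6 | ±27.7 | 3% narrower |
| 40 | 0.8 | ±27.9 | ±27.7 | 0.5% narrower |
| 40 | 1.0 | ±27.3 | ±27.7 | 1.5% wider |
| 60 | 0.5 | ±43.3 | ±41.6 | 4% narrower |

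At N = 23 (15:8) the case with b = 1 is 2.9% wider.

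**The case against.** The strongest reply is that much of the plan is out of sight. The contents list names Section 18.4 as Exploratory Efficacy, and it is redacted. Section 8.5 refers to exploratory efficacy analyses with a carry-forward rule, so such analyses exist. Section 18 sends detailed methods and any inference to a SAP that is not in the supplied text. A reader might therefore infer that the trial has no between-arm estimate at all, or that these endpoints are only tabulated. The documents do not support that. They support the narrower statement that the readable section governing these secondary endpoints does not specify one.

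Second, the tables give n, mean and SD by arm and visit, and Section 18.2 summarizes baseline by arm and eye. A reader could compute a raw-change difference with its interval and see any imbalance. This stands, but a baseline-adjusted estimate and its residual SD cannot be recovered from those tables.

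Third, a reader might infer that raw change wastes much precision. The large-sample variance ratio (1+r)/2 suggests 25% less variance at r = 0.5 and 10% less at r = 0.8. With small-sample terms the figures are about 23% (1 − (0.601/0.683)²) and 7% (1 − (0.416/0.432)²), and the gain can vanish. Nor is chance baseline imbalance a further harm on top: under randomization it is the same variation that makes the raw-change interval wider.

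Fourth, this is a first-in-human safety study without formal testing, and descriptive tables fit that aim. That is true, but an interval without a p-value fits it too.

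**Conclusion.** The point holds as a gap in specification with an inexpensive remedy. Section 18.3.6 does not deliver the comparison with vehicle promised in Section 8.1, or the quantities that Section 8.2 wants for later trials. This is not an error in the safety analysis, and it says nothing about what Section 18.4 or the SAP may contain.

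The main benefit is a stated difference with its uncertainty. At r = 0.5 the half-width is about 0.6 to 0.7 SD, which separate arm means do not show. The extra precision from adjustment is secondary: about 12% at r = 0.5, falling to 1% at r = 0.9. The possible loss is about 1.5% if the slope is 1. These figures rest on 27:13, no dropout, and assumed correlations, slopes and SDs, because the documents give none.

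**What to change.** Add to Section 18.3.6 or the SAP, before database lock, for the expansion cohort:

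- For study-eye CMT (center-subfield measure), macular fluid volume and BCVA, report the EXN407 minus vehicle difference with a 95% CI at each visit where it is measured, with Day 85 as the main time point.
- Estimate it by ANCOVA or a repeated-measures model with the baseline value as covariate. Label it exploratory and give no p-value.
- Use the expansion-cohort vehicle subjects as comparator, and say that this departs from the pooling in Section 8.1. Escalation-cohort vehicle subjects are dosed for 7 days and have no Day 85 visit.
- Report the residual SD for planning.
- State how values after rescue enter the model, consistently with the Synopsis (Stopping Criteria and Rescue Medication) and Section 8.5. Both carry the last observation forward; Section 8.5 does so for exploratory efficacy analyses while safety assessments continue.

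If the SAP or Section 18.4 already contains this, a cross-reference from Section 18.3.6 is enough. The cost is one paragraph and one table per endpoint, with no new visits, measurements or subjects.

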### 18.3.7. Other Safety Assessments

The following assessments will be listed by subject:

- Medical History
- Pregnancy Test/FSH Test
- Physical Examination

18.4.

Term	Percentage
GMOs	~75%
Organic	~95%
Natural	~90%
Artificial	~15%

[REDACTED]

[REDACTED]

[REDACTED]

[REDACTED]

## 18.5. Pharmacokinetics

### 18.5.1. Blood Sample Collections

Plasma concentrations and actual blood sampling times will be listed by treatment and protocol specified time point and summarized using descriptive statistics — number of measurements, arithmetic mean, SD, and coefficient of variance (%CV), geometric mean, minimum, median, and maximum — at each scheduled time point. Individual and mean plasma concentration-time profiles will also be presented graphically for each treatment.

Pharmacokinetic parameters will be computed from the individual plasma concentrations using a non-compartmental approach. Planned analyses of PK data will be described in a separate PK analysis plan which will be appended to the CSR.

## 19. ETHICS

### 19.1. Ethics Review

The final study protocol, including the final version of the ICF, must be approved or given a favorable opinion in writing by an IEC as appropriate. The Investigator must submit written approval to the Sponsor before enrolling any subject into the study.

The PI is responsible for informing the IEC of any amendment to the protocol in accordance with local requirements. In addition, the IEC must approve all advertising used to recruit subjects for the study. The protocol must be re-approved by the IEC upon receipt of amendments and annually, as local regulations require.

The PI is also responsible for providing the IEC with reports of any reportable serious adverse drug reactions from any other study conducted with the study drug (active). The Sponsor will provide this information to the PI.

Progress reports and notifications of serious adverse drug reactions will be provided to the IEC according to local regulations and guidelines.

### 19.2. Ethical Conduct of the Study

The study will be performed in accordance with ethical principles that have their origin in the Declaration of Helsinki (Ethical Principles for Medical Research Involving Human Subjects) and are consistent with ICH GCP applicable regulatory requirements.

### 19.3. Written Informed Consent

The PI will ensure that the subject is given full and adequate oral and written information about the nature, purpose, possible risk and benefit of the study. Subjects must also be notified that they are free to discontinue from the study at any time without prejudice. The subject should be given the opportunity to ask questions and allowed time to consider the information provided before voluntarily signing the written ICF.

The subject's signed and dated informed consent must be obtained before conducting any study procedures. The subjects will be informed of their rights to privacy but will be made aware that the study data will be submitted to the Sponsor and possibly to drug regulatory authorities for review and evaluation. They will be informed also that the study monitor may inspect their medical records to verify the accuracy and completeness of the study records and results.

The acquisition of informed consent should be documented in the subject's medical records, as required, and the ICF will be signed and personally dated by the subject and by the person who conducted the informed consent discussion.

The PI must maintain the original, signed ICF. A copy of the signed ICF must be given to the subject or legal representative. The date that informed consent was signed will be recorded on the eCRF.

## **19.4. Data Protection**

Subjects will be informed that data will be held on file by the Sponsor and that these data may be viewed by staff including the study monitor and by external auditors on behalf of the Sponsor and appropriate regulatory authorities. Subjects will also be informed that a study report will be prepared and may be submitted to regulatory authorities and for publication. However, subjects will be identified in such reports only by study identification number, gender and age. All subject data will be held in strict confidence.

## **20. REGULATORY REQUIREMENTS**

This protocol and any amendment(s) must be submitted to the appropriate regulatory authorities in each respective country, if applicable. A study may not be initiated until all local regulatory requirements are met.

## **21. DATA HANDLING AND RECORDKEEPING**

### **21.1. Inspection of Records**

The Sponsor will be allowed to conduct site visits to the investigation facilities for the purpose of monitoring any aspect of the study. The Investigator agrees to allow the monitor to inspect the drug storage area, study drug stocks, drug accountability records, subject charts and study source documents, and other records relative to study conduct.

### **21.2. Retention of Records**

All source data, clinical records and laboratory data relating to the study will be archived for 15 years after the completion of the study. All data will be available for retrospective review or audit.

Source documents are original documents, data, and records from which the subject's eCRF data are obtained. These include, but are not limited to: hospital records, clinical and office charts, laboratory and pharmacy records, diaries, microfiches, radiographs, angiograms, study drug accountability logs, and correspondence.

The Investigator and study staff are responsible for maintaining a comprehensive filing system of all study-related (essential) documentation. These include but are not limited to: IEC correspondence, study drug accountability logs, and curricula vitae of all personnel participating in the study. These files must be suitable for inspection at any time by the Sponsor, monitor, and/or applicable regulatory authorities. All essential documentation should be retained by the institution as required by the local health authority and IEC.

No study document should be destroyed without prior written agreement between the Sponsor and the Investigator. If the Investigator wishes to assign the study records to another party or move them to another location, the PI must notify the Sponsor in writing of the new responsible person and/or the new location.

### **21.3. Liability/Indemnity/Insurance**

The Sponsor will ensure sufficient insurance is available to enable it to indemnify and hold the Investigator(s) and relevant staff as well as any hospital, institution, ethics committee or the like, harmless from any claims for damages for unexpected injuries, including death, that may be caused by the study drug but only to the extent that the claim is not caused by the fault or negligence of the subjects or Investigator(s).

## **22. PUBLICATION POLICY**

### **22.1. Publication of Results**

The publication, presentation or other public disclosure of study results (each, a “Publication”) will be accurate and honest, undertaken with integrity and transparency and in accordance with the Sponsor’s approval.

Publication of results will be subjected to fair peer-review. Authorship will be discussed between researchers prior to study commencement (or as soon as possible thereafter) and reviewed whenever there are changes in participation.

All conflicts arising through disputes about authorship will be reviewed by the Sponsor. Authorship should be consistent with Good Publication Practices, and International Committee of Medical Journal Editors and relevant local guidelines.

Acknowledgment will be given to collaborating institutions and hospitals and other individuals and organizations providing finance or facilities. Subject confidentiality will be maintained by referring to individual subjects by their identifying code used in the trial. Data will not be released publicly until the manuscript is accepted for publication. In the case of no publication, information will only be released to the public and media in accordance with the Sponsor’s approval.

Study data that have not been published, presented or otherwise disclosed in accordance with the clinical trial agreement shall remain confidential information of the Sponsor, the Investigator may not disclose or permit the disclosure of such unpublished data to any third party, nor may they disclose or permit the disclosure of any study data to any third party in greater detail than the same have been disclosed in any permitted publication, presentation or other disclosure.

The results summary will be posted to registries as required per local laws or regulations.

